4.3 Number of Participants

Approximately 71 participants will be enrolled in the study. This includes 5 in the Phase 1 portion and approximately 66 in the Phase 2 portion

4.4 Replacement of Participants

In Phase 1, if a subject is withdrawn from the study prior to completing GC4711/Radiotherapy and 30 days of follow-up without experiencing a DLT prior to withdrawal, an additional subject may be added.

In Phase 2, patients who are randomized but do not receive study drug may be replaced.

4.5 Number of Sites

Phase 1: Up to 4 sites in the US will participate in the Phase 1 portion.

Phase 2: Up to 20 sites in the US will participate in the Phase 2 portion.

4.6 End of Study Definition

End of Study (Individual Participant): A participant is considered to have ended participation in the study if he/she has completed all phases of the study including the month 24 follow-up or who has withdrawn consent from all study participation or who has died.

Primary Completion: The primary completion date is defined as the date when the last participant is assessed or receives an intervention for the final collection of data for the primary endpoint(s) for the purposes of conducting the primary analysis. For Phase 1, this is defined as 30 days post SBRT. For the Phase 2, this is defined as 6 months post SBRT.

End of Study (End of trial): The date the final participant was examined or received an intervention/assessment for purposes of final collection of data for the primary, secondary or exploratory outcome measures.

4.7 Rationale for Study Design

In non-clinical development, GC4711 has shown the potential of increasing efficacy of high dose RT as well as limit associated inflammatory and fibrotic normal tissue reactions. As SBRT is a commonly used high dose RT treatment for early NSCLC, in this trial, we combine

GC4711/placebo with this national standard SBRT indication. Though SBRT has been shown to be effective in the treatment of small peripheral NSCLC (Timmerman 2010), its use for larger and/or central lesions has been associated with an increased risk of toxicity and less favorable local control (Stanic 2014, Bezzak 2015). By combining GC4711 with the 5-fraction regimen (Timmerman 2006, Lo 2010, Ettinger 2020), this study will assess both tolerability of the regimen and disease control. In addition to the routine efficacy parameters of local and regional control, control of distant metastatic rate, progression free survival (PFS) and overall survival (OS), we will also examine the effects of SBRT and GC4711 on response rate by the RECIST 1.1 criteria and degree of in-field tumor response.

Lung damage is the most common reported adverse effect and close monitoring of pneumonitis in this trial can be compared to extensive historical data (Timmerman 2006, 2010 and 2018). Radiation induced injury is a slow developing process, showing most radiological changes and symptoms around 3-6 months after treatment (Takeda 2013, Videtic 2013, Jain 2018, Ferrero 2015). Approximately 25% of patients treated with a 5-fraction regimen of SBRT encounter lung function decline (Stone 2015), of which a small portion (mean 10%) remain with a significant decline, which can be difficult to distinguish from recurrence (Huang 2012). Radiological changes have been described in larger number of subjects but are not always translated in clinical symptoms. Safety of GC4711 is the primary endpoint of the phase 1 portion and acute and late RT toxicities, as well as disease outcome are monitored as secondary endpoints in phase 2.

4.8 Rationale for GC4711 Starting Dose

The proposed dosing regimen for this study will consist of 100 mg IV of GC4711 administered over 15 minutes prior to each SBRT fraction. Patients will be required to receive a total of 3 x 18-20 Gy or 5 x 10-12 Gy for a total 50 to 60 Gy. Following the healthy human volunteer study (GTI-4711-002), IV administration of GC4711 was found to be well-tolerated following a single administration at dose levels up to 120 mg and following repeated dosing of 90 mg/day for 14 days or a total weekly dose of 630 mg. Therefore, GC4711 at a dose of 100 mg x 3 or 5 doses (aligning with SBRT regimen) is expected to be tolerated by this patient population.

This dose level is also supported by nonclinical safety studies. Based on the STD10 (the dose in non-clinical studies that was severely toxic to 10% of the rodents) and the highest non-severely toxic dose (HNSTD) calculations using the GLP 14-day rat (Study 1324-4711-0520) and dog (Study 1325-4711-0520) toxicology studies, a 90 to 96 mg/patient starting dose of GC4711 are supported.

Further, GTI-4711-001 demonstrated substantially similar safety and pharmacokinetics of GC4711 and GC4419. Acceptable safety of a 90 mg dose of GC4419 (approximately equimolar to 100 mg of GC4711) has been observed with GC4419 administered to head and neck cancer patients, M-F for up to 7 weeks, in combination with intensity-modulated radiotherapy (IMRT) and concurrent cisplatin (Anderson 2019). Adverse effects associated with either drug have been transient in clinical trials or have not appeared to be worse with repeat dosing (Anderson 2019).

5 SELECTION AND WITHDRAWAL OF SUBJECTS

Before any study-specific activities/procedures, the appropriate written informed consent must be obtained (see Appendix 1).

5.1 Inclusion Criteria

Participants are eligible to be included in the study only if all the following criteria apply:

1. Male or female subjects at least 18 years of age.
2. Ability to understand and the willingness to sign a written informed consent.
3. Histological or biopsy proven NSCLC. For peripheral lesions, cytology and/or clear imaging-guided suspicion is accepted if histology cannot be obtained.
4. ECOG performance status of 0-3.
5. Lymph node negative (T1 to T3N0M0), centrally located (within 2cm in all directions around the proximal bronchial tree, including ultra-central tumors, abutting the bronchial tree or trachea) or large (>1-7cm) Non-Small Cell Lung Cancer (NSCLC) , judged acceptable for SBRT by the treating Investigator. Staged with FDG-PET/CT, brain CT or MRI with contrast and/or mediastinoscopy, measurable disease as defined by RECIST 1.1. (See Figure 2 below).
6. Adequate end-organ function, based on routine clinical and laboratory workup:
 - a. ANC >1,000 cells/ μ l, Platelets \geq 75,000 cells/ μ l, Hemoglobin \geq 8.0 g/dl
 - b. Serum creatinine \leq 2 mg/dL or calculated creatinine clearance \geq 30 ml/min
 - c. Total bilirubin \leq 1.5 x ULN (or direct bilirubin below the ULN), AST and ALT \leq 2.5 x ULN
 - d. International normalized ratio (INR) (or prothrombin time (PT)) and activated partial thromboplastin time (aPTT) \leq 1.5 x ULN unless participant is receiving anticoagulant therapy, if values are within the intended therapeutic range
7. Males and females of must agree to use effective contraception starting prior to the first day of treatment and continuing after the last dose of GC4711/Placebo for 30 days (females) and 90 days (males).

[figure not shown]

Figure 2 Anatomy of central and ultra-central lung tumors

Timmerman and colleagues defined central lung tumors as those located within 2 cm of the proximal bronchial tree (Timmerman 2006). Here defined ultra-central lung tumors as those abutting the proximal bronchial tree or trachea (Lo 2010, Chaudhuri 2015, Chang 2018).

5.2 Exclusion Criteria

Participants are excluded from the study if any of the following criteria apply:

1. Subjects with confirmed nodal and/or distant disease (including brain), according to standard workup by local investigator.
2. Subjects with peripheral lesions of 1cm or smaller
3. Prior treatment with immunotherapy within 3 months prior to Day 1 dosing.
4. Prior intra-thoracic radiotherapy or surgery with substantial overlap to planned in former radiation fields as determined by the treating radiation oncologist.
5. Subjects not recovered/controlled from prior treatment-related (chemotherapy or targeted therapy) toxicities judged by treating physician.
6. Uncontrolled malignancy other than lung cancer that requires active treatment or is deemed by the treating physicians to be likely to affect the subject's survival duration.
7. History of allergic reactions attributed to compounds of similar chemical or biologic composition to GC4711.
8. Uncontrolled intercurrent illness including, but not limited to, active infection, symptomatic congestive heart failure, unstable angina pectoris, cardiac arrhythmia, or psychiatric illness/social situations that, in the opinion of the investigator, would limit compliance with study requirements.
9. Participation in other clinical trials actively testing new anti-cancer treatments unless previous written approval provided by the Sponsor.
10. Requirement for concurrent treatment with nitrates or other drugs that may, in the judgment of the treating investigator, create a risk for a precipitous decrease in blood pressure.

11. Female subjects who are pregnant or breastfeeding.
12. Any other conditions that, in the Investigator's opinion, might indicate the subject to be unsuitable for the study.

5.3 Screen Failures

A subject is considered as a screen failure if the subject signs the ICF but withdraws consent or is deemed ineligible prior to registration/randomization. The reason why the subject was precluded from the clinical study will be recorded in the medical record and eCRF. Individuals who do not meet the criteria for participation in this study (screen failure) may be rescreened.

5.4 Discontinuation of Study Intervention and Participant Discontinuation/Withdrawal

Subject Study Withdrawal: A subject has the right to withdraw from the study at any time for any reason. Subjects who withdraw consent from study treatment and/or study assessments early should be encouraged to continue with survival and late toxicity follow-up, if feasible.

Subject Study Discontinuation: The Investigator or Sponsor may also, at his/her discretion, discontinue a subject from participating in this study at any time.

Study Intervention Discontinuation: A subject may discontinue study treatment but remain in the study for follow-up for any of following reasons:

- A protocol violation (reason must be specified, for example: lack of compliance, use of a prohibited concomitant medication, failure to meet inclusion/exclusion criteria after study entry, etc.)
- The subject was “lost to follow-up”
- Unacceptable adverse event necessitating treatment cessation
- More than three infusion modifications of GC4711/placebo
- Subject requests to withdrawal from the study treatment
- Subject becomes pregnant
- Other reasons (reason must be specified, for example: the subject moved, investigator decision, Sponsor decision to terminate trial, etc.)

If a subject discontinues from the study treatment early (did not complete SBRT regimen and/or receive all protocol required infusions of study drug), they will continue to be followed for progression, toxicities and survival as outlined in the SOA.

The primary reason and date for ceasing treatment, discontinuation and/or subject withdrawal will be clearly documented in the subject's medical record and recorded on the appropriate CRF page.

Discontinuation of specific study sites or of the study are handled as part of

Appendix 1.

6 INVESTIGATIONAL PRODUCT AND TREATMENT OF SUBJECTS

Study intervention is defined as any investigational intervention(s), marketed product(s), placebo, or medical device(s) intended to be administered to a study participant according to the study protocol.

Refer to the GC4711 IB and Pharmacy Manual for more detailed information regarding the storage, preparation, destruction, and administration of each treatment.

The site pharmacists will be unblinded to the treatment assignments. The Principal Investigator and remainder of the site staff will be blinded to treatment assignment. The Unblinded Pharmacist should take every precaution to prepare the study treatment in a blinded fashion and out of site from the Blinded site clinical staff. The Blinded Clinical Staff should be mindful of the steps in place to maintain the blind.

6.1 Investigational Product: GC4711/Placebo

GC4711 Dosage Formulation and Preparation

GC4711 IV drug product is formulated as a lyophilized solid in a vial and reconstituted shortly before administration with a provided 26 mM sodium bicarbonate aqueous buffer diluent. Sterile drug product and diluent will be provided by Galera Therapeutics Inc., and the drug product will be supplied as 120 mg in 3 mL clear glass vials and reconstituted by adding 1.10 mL of the provided diluent to yield 100 mg/mL reconstituted drug product. GC4711 (reconstituted solution) will be prepared by the unblinded pharmacist, diluted in normal saline (0.9% NaCl) to obtain a 100 mL dosing solution for IV infusion. 100 mL Normal saline (0.9% NaCl) for IV infusion, supplied by the site, will be used as placebo.

GC4711 Dosage, Administration, and Schedule

Phase 1:

100 mg/day of GC4711 IV will be given over 15 minutes, starting from the first to the last SBRT treatment. GC4711 will be given before SBRT with a maximum of 180 minutes between end of infusion and the start of SBRT.

Phase 2:

- **Arm A:** 100 mg/day of GC4711 will be given via IV infusion over 15 minutes, prior to each SBRT dose, from the first to the last SBRT treatment. On days of SBRT, GC4711 will be administered with a maximum of 180 minutes between the end of infusion and the start of SBRT.

- **Arm B:** Placebo (normal saline) will be administered via IV infusion over 15 minutes to be completed with a maximum of 180 minutes prior to SBRT as for Arm A.

A total of 100 mL of GC4711 or Placebo (normal saline) will be infused IV over a 15-minute period using a programmable pump, when feasible. Each infusion should be given before each of the SBRT treatments ([Table 1 Schedule of Activities](#)). In situations where SBRT is not given following study drug infusion, an additional dose of GC4711/placebo may be given prior to the rescheduled fraction.

GC4711 Drug Packaging and Labeling

GC4711 with diluent will be provided by Galera as single-use vials for daily doses to be administered IV concurrent with SBRT. The drug product is supplied as 120 mg in 3 mL clear glass vials along with 26 mM sodium bicarbonate buffer diluent which is packaged in a 3 mL clear glass vial. Each vial will be labeled with the appropriate language, including the required regulatory text.

Normal saline will be provided and prepared by the site institutional pharmacy for subjects assigned to placebo in the Phase 2 portion of the study.

Maintenance of the Blind

All staff at the site should be designated as either blinded or unblinded. For Phase 2, the site pharmacists will be unblinded to the treatment assignments assigned within the Randomization and Trial Supply Management (RTSM) System.

Unblinded pharmacy staff will be responsible for management and accountability of investigational product and preparation of study drug in a blinded fashion. The unblinded pharmacy staff will ensure the double-blind nature of this study and will not share the treatment assignment directly or indirectly (IP Accountability Logs, IV bag labels, etc.) with the blinded site staff. Sites should be able to provide documentation regarding how the blind is maintained at their sites.

The site pharmacists will obtain treatment assignments for subjects via the Randomization and Trial Supply Management System (RTSM) through their unique username and password, which should not be shared. Blinded staff will not have access to the treatment assignments via the RTSM. Preparation of the assigned treatment group (GC4711 or placebo) can also be found in the Pharmacy Manual.

Investigational Product Storage and Accountability

GC4711 should be stored in the pharmacy at -15°C to -25°C. The sodium bicarbonate aqueous buffer diluent will also be stored in the pharmacy. The diluent must be stored under refrigerated conditions (2 to 8°C) and must not be frozen. The storage temperature should be monitored and recorded daily as per site SOPs to ensure temperatures are maintained per above. Copies of

temperature monitoring logs will be made available to the CRA upon request. The sponsor must be notified of any deviation from the specified storage conditions.

Study drug must always be kept in a secure place with access limited to the unblinded pharmacy staff under the appropriate storage conditions. All unblind personnel involved in the dispensing of study drug should be aware of its location. Any deviations in accountability and/or storage should be reported to the site CRA immediately.

Study Intervention Compliance

Study drug will be administered under the supervision of study site personnel. The infusion volume and timing of each dose will be recorded. Accidental overdoses should be reported to the Sponsor/designee promptly.

6.2 Stereotactic Body Radiation Therapy (SBRT)

SBRT Dosage, Administration, and Schedule

Patients will be evaluated by the treating radiation oncologist at the local site. Based on location and size of the tumor, dose planning will be determined by clinical appropriateness that balances ablation of the lesion(s) while respecting normal tissue constraints including for ultra-central lesions the volume criterium of the contoured proximal bronchial tree less than 0.03cc =<52.5Gy (Bejzak 2019).

Table 2 Organ Constraints for a 3-Fraction SBRT Regimen

Serial Tissue	Volume (cc)	Volume Max (Gy)	Max Point Dose (Gy) ²	Endpoint (\geq Grade 3)
Esophagus ¹	<5	27.9	32.4	Esophagitis
Brachial Plexus	<3	22	26	Neuropathy
Heart/Pericardium	<15	24	30	Pericarditis
Great vessels	<10	39	45	Aneurysm
Trachea and Large Bronchus ¹	<5	39	43	Impairment of pulmonary toilet
Bronchus smaller airways	<0.5	25.8	30	Stenosis with atelectasis
Rib	<5	40	50	Pain or fracture
Lung (Right & Left)	1500 for males; 950 for females ³	10.8		Basic Lung Function
Lung (Right & Left)			V-11.4Gy<37%	Pneumonitis
Spinal cord	<0.35	15.9	22.5	Myelitis

Abbreviations:

1. Avoid circumferential irradiation

2. “point” defined as 0.035cc or less

3. or one-third of the “native” total organ volume (prior to any resection or volume reducing disease), whichever is greater:

- Exceeding these dose tolerances by more than 2.5% constitutes a minor protocol violation.

- Exceeding these dose tolerances by more than 5% constitutes a major protocol violation.

Table 3 Organ Constraints for a 5-Fraction SBRT Regimen

Serial Tissue	Volume (cc)	Volume Max (Gy)	Max Point Dose (Gy) ²	Endpoint (\geq Grade 3)
Esophagus ¹	<5	32.5	38	Esophagitis
Brachial Plexus	<3	27	32.5	Neuropathy
Heart/Pericardium	<15	32	38	Pericarditis
Great vessels	<10	47	53	Aneurysm
Trachea and Large Bronchus ¹	<5	45	50	Impairment of pulmonary toilet
Bronchus smaller airways	<0.5	32	40	Stenosis with atelectasis
Rib	<5	45	57	Pain or fracture
Lung (Right & Left)	1500 for males; 950 for females ³	12.5		Basic Lung Function
Lung (Right & Left)			V-13.5Gy<37%	Pneumonitis
Spinal cord	<0.35	22	28	Myelitis

Abbreviations:

1. Avoid circumferential irradiation
2. “point” defined as 0.035cc or less
3. or one-third of the “native” total organ volume (prior to any resection or volume reducing disease), whichever is greater:
 - Exceeding these dose tolerances by more than 2.5% constitutes a minor protocol violation.
 - Exceeding these dose tolerances by more than 5% constitutes a major protocol violation.

By protocol prescription, the RT regimen consists of a 5-fraction treatment with doses between 10-12 Gy per fraction (Bejzak 2015) or 3-fraction treatment with doses of 18-20 Gy per fraction to the FDG-PET+ areas delineated as gross tumor volume (GTV). This target volume can be translated into an iGTV by including correction for 4D movement, no clinical target margins (CTV) are used. An additional 0.5 cm in the axial plane and longitudinal plane (craniocaudal) will be added to the GTV to constitute the planning target volume (PTV), while iGTV is reconstructed a 0.3cm margin is accepted. Larger margins may be used in cases where greater motion of the hemidiaphragm is observed in simulation despite standard maneuvers to diminish motion. No (nodal) elective field is given.

For purposes of dose planning and calculation of monitor units for actual treatment, this protocol will require tissue density heterogeneity correction. Successful treatment planning will require accomplishment of all the following criteria:

- Maximum dose: The treatment plan should be created such that 100% (60Gy) corresponds to the maximum dose delivered to the patient. This point must exist within the PTV.
- Prescription isodose: The prescription isodose surface must be >60% and < 90% of the maximum dose (60 Gy) covering the PTV.
- Prescription Isodose Surface Coverage: The prescription isodose surface will be chosen such that 95% of the PTV is conformally covered by the prescription isodose surface (PTV

V95%RX=100%) and 99% of PTV receives a minimum of 90% of the prescription dose (PTV V90%RX>99%).

Fractions should be given within 180 minutes from the end of the GC4711/placebo infusion. A minimum of 18 and maximum of 72 hours is permitted between fractions. Additionally, in case of machine break-down a 96-hour window is allowed. All fractions must be given within a maximum of 10 calendar days (+3 days in the case of a holiday or technical issue).

If SBRT administration is interrupted on any given day due to a machine break-down or other unforeseen circumstances, the rest of the treatment or a new SBRT session must be given as soon as possible. Rescheduling and SBRT dosing will be determined by the patient's treating physician in accordance with standard of care and covered with extra GC4711/placebo dosing. In case of a 6th fraction and/or dose of GC4711/Placebo may be given.

Anti-emetic and anti-diarrheal prophylaxis and hematopoietic growth factor use should be administered per ASCO guidelines.

Critical Organ Dose-Volume Limits

In order to verify dose-volume limits, the organs must be contoured such that appropriate dose volume histograms can be generated. Instructions for the contouring of these organs are as follows:

- **Spinal Cord:** contoured based on the bony limits of the spinal canal. The spinal cord should be contoured starting at least 10 cm above the superior extent of the PTV and continuing every CT slice to at least 10 below the inferior extent of the PTV.
- **Esophagus:** contoured using mediastinal windowing on CT to correspond to the mucosal, submucosa, and all muscular layers out to the fatty adventitia. The esophagus should be contoured starting at least 10 cm above the superior extent of the PTV and continuing every CT slice to at least 10 below the inferior extent of the PTV.
- **Brachial Plexus:** defined ipsilateral brachial plexus originates from the spinal nerves exiting the neuroforamina on the involved side from around C5 to T2. However, for the purposes of this protocol, only the major trunks of the brachial plexus will be contoured using the subclavian and axillary vessels as a surrogate for identifying the location of the brachial plexus. This neurovascular complex will be contoured starting proximally at the bifurcation of the brachiocephalic trunk into the jugular/subclavian veins (or carotid/subclavian arteries) and following along the route of the subclavian vein to the axillary vein ending after the neurovascular structures cross the second rib.
- **Heart:** contoured along with the pericardial sac. The superior aspect (or base) for purposes of contouring will begin at the level of the inferior aspect of the aortic arch (aortopulmonary window) and extend inferiorly to the apex of the heart.
- **Trachea and Proximal Bronchial Tree:** contoured as two separate structures using mediastinal windows on CT to correspond to the mucosal, submucosa and cartilage rings and airway channels associated with these structures. For this purpose, the trachea will be

divided into two sections: the proximal trachea and the distal 2 cm of trachea. The proximal trachea will be contoured as one structure, and the distal 2 cm of trachea will be included in the structure identified as proximal bronchial tree. Differentiating these structures in this fashion will facilitate the eligibility requirement for excluding patients with tumors within 2 cm of the proximal bronchial tree (see below).

- **Proximal Trachea:** Contouring of the proximal trachea should begin at least 10 cm superior to the extent of the PTV or 5 cm superior to the carina (whichever is more superior) and continue inferiorly to the superior aspect of the proximal bronchial tree (see the diagram definitions below).
- **Proximal Bronchial Tree:** include the most inferior 2 cm of distal trachea and the proximal airways on both sides as indicated in the diagram in Figure 2. The following airways will be included according to standard anatomic relationships: the distal 2 cm of RTOG 0618 (Timmerman 2018) trachea, the carina, the right and left mainstem bronchi, the right and left upper lobe bronchi, the intermedius bronchus, the right middle lobe bronchus, the lingular bronchus, and the right and left lower lobe bronchi. Contouring of the lobar bronchi will end immediately at the site of a segmental bifurcation.
- **Whole Lung:** Planning CT need to cover both entire lung volumes. Both the right and left lungs should be contoured as one structure. Contouring should be carried out using pulmonary windows. All inflated and collapsed lung should be contoured; however, gross tumor (GTV) and trachea/ipsilateral bronchus as defined above should not be included in this structure.
- **Skin:** defined as the outer 0.5 cm of the body surface. As such it is a rind of uniform thickness (0.5 cm) which envelopes the entire body in the axial planes. The cranial and caudal surface of the superior and inferior limits of the planning CT should not be contoured as skin unless skin is present in these locations (e.g., the scalp on the top of the head).
- All relevant normal tissue structures (e.g. spinal cord, lungs, heart, esophagus, brachial plexus, trachea and proximal bronchial tree, skin, etc.) are required in both planning images, as well as dose-volume histogram, for further contouring help see RTOG contouring atlas (<https://www.rtog.org/CoreLab/ContouringAtlases/LungAtlas.aspx>).

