The RTOG 0813 trial identified SBRT dosing of 11.5 or 12 Gy x 5 fractions as associated with acceptable toxicity and with approximate 2-year rates for local control, overall survival, and progression-free survival of approximately 90%, 70%, and 55%, respectively ([Bezjak 2019](#)). Other studies ([Stone 2015](#), [Mohamad 2018](#)) reported control rates around 70% and PFS 50-60% at 2 years.

Radiation-induced lung injury is a slowly developing process, mostly manifesting as radiological changes only and transient symptoms around 4-6 months (mean 135 days) after treatment ([Jain 2018](#), [Ferrero 2015](#)). Clinically scored and symptomatic pneumonitis is seen in approximately 10% of patients 6 months after SBRT ([Kang 2015](#), [Yamashita 2014](#), [Mohamad 2018](#)). [Stone et al \(2015\)](#) referred to DLCO decline as the most objective measure of lung toxicity, referring to an observed decline (grade 1 or more) in 20-30% of patients. While a small decline is not seen as clinically significant, it is predictive for more severe accumulative toxicity risk in cases of pre-existing lung disease or in those with subsequent need for re-treatment in the thoracic area. Radiological changes in lung parenchyma are observed in over 40% of SBRT patients ([Kimura 2006](#), [Timmerman 2018](#)).

Approximately a 25% of patients experience declines in DLCO, reported after a 5-fraction regimen SBRT ([Stone 2015](#)). Slow decline in lung function and radiological changes are described after SABR/SBRT leaving a small portion of patients (mean 10%) with persistent significant decline at one year, which can be difficult to distinguish from recurrence ([Huang 2012](#)). Both lung function testing and radiographical changes are directly related clinical scoring at 3 months ([Tadasuke 2020](#)), explaining a gradual change from radiological to functional and finally clinical symptomatic SBRT complication related to dose and volume treated.

Both radiological and clinical data are needed to create future guidelines around lung SBRT ([Mohamad 2018](#), [Tadasuke 2020](#), [Palma 2013](#)). Complementary drugs such as GC4711 may add important value by increasing efficacy and reducing pneumonitis risk.

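### Section 6.2 fixes every plan's maximum at 60 Gy and its prescription isodose between 36 and 54 Gy; if the regimen dose is prescribed at that isodose, most permitted 5-fraction doses and all 3-fraction doses are excluded

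*Combined protocol and SAP*

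**What the plan says.** Section 4.8 gives the required dose as "3 x 18-20 Gy or 5 x 10-12 Gy for a total 50 to 60 Gy". Section 6.2 (Stereotactic Body Radiation Therapy) repeats the two regimens, introduces them as the protocol's prescription, and directs the dose to the tumour: "3-fraction treatment with doses of 18-20 Gy per fraction to the FDG-PET+ areas delineated as gross tumor volume (GTV".

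The planning criteria follow, under the lead-in "Successful treatment planning will require accomplishment of all the following criteria". Three bullets matter here.

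- **Maximum dose:** "The treatment plan should be created such that 100% (60Gy) corresponds to the maximum dose delivered to the patient". This point must lie inside the PTV.
- **Prescription isodose:** "The prescription isodose surface must be >60% and < 90% of the maximum dose (60 Gy) covering the PTV".
- **Coverage:** in words, 95% of the PTV is to be covered by the prescription isodose. The bracketed shorthand and the second condition read "V95%RX=100%) and 99% of PTV receives a minimum of 90% of the prescription dose".

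The 60 Gy figure appears in two of the bullets. It is not tied to one regimen or dose level, and it is not called an example.

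**The concern.** The permitted totals run from 50 to 60 Gy, but the planning rule is anchored to the single value of 60 Gy. A prescription isodose below 90% of a 60 Gy maximum cannot deliver 54 Gy or more, and most of the permitted range lies at or above 54 Gy. A site that follows the bullets literally cannot plan much of what Sections 4.8 and 6.2 allow. A site that follows the regimen sentence may break the bullets.

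What is at stake is a uniform, checkable dose. In-field response is the Phase 2 primary endpoint, and dosimetry enters the exploratory risk-factor analysis for lung injury (Section 3). Phase 2 may use up to 20 sites (Section 4.5), while Section 4.1 marks the radiotherapy quality-assurance information as Phase 1 only. If sites settle the conflict differently, the same regimen label need not describe the same dose to the PTV.

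**Working it through.** **Inputs.** Section 6.2: 5 fractions of 10-12 Gy or 3 fractions of 18-20 Gy; plan maximum 60 Gy; prescription isodose >60% and <90% of 60 Gy. Section 4.8: total 50 to 60 Gy.

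**Step 1. Reproduce the stated total** (fractions x dose per fraction). 5 x 10 = 50, 5 x 12 = 60, 3 x 18 = 54 and 3 x 20 = 60 Gy. Together these span 50 to 60 Gy, as Section 4.8 states.

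**Step 2. Isodose window.** 0.60 x 60 = 36 Gy and 0.90 x 60 = 54 Gy, both bounds excluded.

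**Step 3. Regimen dose taken at the prescription isodose.** The total must be below 54 Gy.

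- 5 fractions: 54 / 5 = 10.8, so 10 to <10.8 Gy per fraction complies. Share of the range: (10.8 - 10) / (12 - 10) = 0.40.
- 3 fractions: 54 / 3 = 18, and the range starts at 18, so none complies. 3 x 18 Gy is exactly 90% and fails only on the strict inequality, as does 5 x 10.8 Gy.

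**Step 4. Regimen dose taken as the plan maximum.** The total must equal 60 Gy: 60 / 5 = 12 and 60 / 3 = 20. Only the top dose of each regimen complies.

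| Regimen | Total (Gy) | % of 60 Gy | Complies at isodose | Complies as maximum |
|---|---|---|---|---|
| 5 x 10 | 50 | 83.3 | yes | no |
| 5 x 11 | 55 | 91.7 | no | no |
| 5 x 12 | 60 | 100 | no | yes |
| 3 x 18 | 54 | 90.0 | no (strict bound) | no |
| 3 x 19 | 57 | 95.0 | no | no |
| 3 x 20 | 60 | 100 | no | yes |

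**Step 5. Regimen dose taken as a GTV dose.** A GTV dose of 50 to just under 60 Gy, a 60 Gy maximum inside the PTV and a covering isodose of 36-54 Gy can coexist, with 5 x 12 and 3 x 20 Gy at the limit. There is no numerical conflict, but no bullet says what GTV dose must be achieved.

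**Step 6. Coverage shorthand.** V90%RX>99% matches its own words: more than 99% of the PTV at 90% of the prescription dose. In the same notation, V95%RX=100% means the whole PTV at 95% of the dose. The words ask for 95% of the PTV at the full prescription isodose, which is V100%RX=95%.

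**Step 7. Plan maxima if 60 Gy is removed and the 60-90% window is kept** (prescription / 0.90 to prescription / 0.60).

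- 50 Gy: 55.6 to 83.3 Gy
- 54 Gy: 60 to 90 Gy
- 60 Gy: 66.7 to 100 Gy

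**The case against.** The strongest reply is the GTV reading in Step 5. Section 6.2 does name the GTV as the place the dose goes. The GTV lies inside the PTV and need not receive the maximum, so on that reading the numbers are compatible. A reader might infer from the bullets that the permitted doses cannot be reconciled with the rule on any reading, or that no dose complies. The documents do not support either inference: the GTV reading is not excluded, and some doses comply on each of the other two. The cost of the GTV reading is that prescription must mean a GTV dose in the regimen sentence and a PTV-covering dose in the bullets, with no criterion for the former. That makes it the less natural reading, not an impossible one.

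A second reply is that 60 Gy only illustrates a top-dose plan, and that the maximum-dose bullet says should. The text does not call it illustrative, the isodose bullet says must and repeats 60 Gy, and the lead-in requires every criterion.

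It is also tempting to treat the cited trial as proof that 60 Gy is the mistake: "The RTOG 0813 trial identified SBRT dosing of 11.5 or 12 Gy x 5 fractions as associated with acceptable toxicity". Its totals, 57.5 and 60 Gy, exceed 54 Gy. But the protocol does not say where that trial specified its dose, so this is at most suggestive.

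The practical safeguards stand. The treating radiation oncologist sets the plan, the organ limits in Tables 2 and 3 remain in force, and the minor and major violation thresholds attach to those limits rather than to these bullets.

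**Conclusion.** The planning rule is wrong as written on its natural reading, and it should be corrected. With the regimen dose at the prescription isodose, 40% of the width of the 5-fraction range complies and none of the 3-fraction range. With the regimen dose as the plan maximum, one dose per regimen complies. These are shares of the dose range, not of patients, because the documents give no split of patients by regimen or dose.

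The conclusion assumes that 60 Gy applies to every plan and that prescription has one meaning throughout the planning text. If the sponsor means a GTV dose, the numerical conflict disappears and a missing specification remains.

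A reader might also infer that patients were misdosed or that the treatment comparison is biased. Nothing in the documents shows misdosing. Assignment is randomized and blinded, so no between-arm bias is claimed, and the sample size and 90% confidence interval are unaffected.

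**What to change.** Amend the planning criteria in Section 6.2 as follows.

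1. Maximum dose: 100% is the plan's own maximum point dose, which must lie within the PTV.
2. Prescription isodose: the 5 x 10-12 Gy or 3 x 18-20 Gy dose is prescribed to the isodose surface covering 95% of the PTV, and that surface must be >60% and <90% of the plan maximum. Delete both 60 Gy figures.
3. Align the sentence that directs the dose to the GTV with item 2.
4. Replace V95%RX=100% with V100%RX=95%.

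The downside is that the 60 Gy cap goes. The window alone would then allow the maxima in Step 7. Ultra-central tumours are eligible (Section 5.1). Tables 2 and 3 and the airway limit ("the volume criterium of the contoured proximal bronchial tree less than 0.03cc =<52.5Gy") still bind, but the sponsor's radiation oncologists must confirm the window or set a cap for each regimen before release.

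Other intentions need other repairs. If the regimen dose is meant to be the plan maximum, replace 60 Gy with the plan's own total; the isodose window is then 30-45 Gy for a 50 Gy plan and 36-54 Gy for a 60 Gy plan. If a GTV dose is meant, say so and give a GTV criterion. Restricting treatment to 5 fractions of 10 to <10.8 Gy and dropping 3 fractions is needed only if 60 Gy is kept and the dose is at the prescription isodose.

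The cost is a protocol amendment with IRB/IEC approval (Appendix 1), radiation-oncology sign-off and a site memo. It needs no extra patients or procedures and no change to the analysis.

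A separate, minor item can go in the same amendment. The longest gap between fractions is 72 hours in Section 6.2, with 96 hours for machine breakdown, but 96 hours without that condition in the Synopsis, Section 4.1 and the Table 1 footnote. The overall-time allowance is +3 days in the Synopsis, the Phase 2 text of Section 4.1 and Section 6.2, but +5 days in the general text of Section 4.1 and the Table 1 footnote. Choose one rule for each and use it throughout.
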